10.8.3 Secondary Analyses

Acceptability

To assess product preference of the study product, the number and percentage of participants who report that they prefer the ring at least as much as other HIV prevention methods (e.g., condom) will be calculated by arm.

Adherence

The average rate of VR use will be calculated in both arms along with 95% confidence intervals. These rates will be based on participant's self-report of product use at 4, 8, and 12 weeks. The difference between adherence rates with its corresponding 95%

confidence interval will be used to assess adherence of the study product compared to placebo.

Pharmacokinetics

A population mean and standard deviation of the end-of-period dapivirine concentrations for each woman will be calculated based on the samples obtained as described above. The population mean from this study will be compared to the population mean and standard deviation from similar end of period dapivirine results for each matrix – plasma, vaginal fluid, and cervical tissue – in MTN-013.

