10.4.2 Secondary Endpoints

Acceptability Endpoint

To evaluate acceptability, the proportion of participants who at their 12-Week Final Clinic Visit report via acceptability questionnaire that they prefer the ring at least as much as other HIV prevention methods. A sample size of 72 females receiving the dapivirine VR will provide an absolute precision of 10.5% (i.e., half the width of the 95% confidence interval) assuming an observed acceptability of 75%.

Adherence Endpoint

Adherence will be measured by the percentage of women who keep the VR inserted at all times in the vagina over the course of 12 weeks. A sample size of 96 women will provide an absolute precision of 9.1% (i.e., half the width of the 95% confidence interval) assuming an observed adherence of 75%.

Pharmacokinetic Endpoints

The PK endpoint is a description of the end of period (28 day post ring insertion) plasma, vaginal fluid, and cervical tissue dapivirine concentrations at week 4, 8, and 12 which will be compared to the same results in a recently studied population of premenopausal adult women (MTN-013). The 28 day assessment in each ring period – just before ring removal – represents near steady-state concentrations in prior dapivirine ring studies. The intent is to determine if the plasma and vaginal fluid dapivirine concentrations are different in postmenopausal women than in premenopausal adult women after placement of dapivirine vaginal rings. The vaginal fluid will be collected by tear strip and the cervical tissue will be collected by biopsy in only a subset of women, 45 for tear strip and 15 for biopsy. This more intensively sampled subset was selected to provide a richer dataset of sampling from the female genital tract and chosen to balance feasible logistical complexity which demands a simpler, more sparse sampling approach with the low likelihood of an important difference between postmenopausal and premenopausal adult populations.

Approximately 45 women will provide vaginal fluid. The CV% ranges from 118% to 153% depending on time, location, and formulation. Also, there is no evidence of dose-proportionality for the increase from 0.001% dapivirine gel to 0.005% gel, there is no increase (due to either no difference or insufficient power to detect the difference). If one assumes a CV% of 130%, and comparison of MTN-013 (N=12) to MTN-024 (N=22), then with 5% type I error and 80% power, we can exclude a difference as large as 1.04 SD units or a 135% difference.

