Approximately 15 women will provide cervical tissue. There are insufficient data published to estimate CV%, but it appears to be quite large. Nel²⁶ reports a range of tissue dapivirine concentration from 1-43, 1-190, and 1-356 for 0.001, 0.005, and 0.02% dapivirine gel, respectively. If this had the same variation as tenofovir in tissue, the CV% would be 210-240%. So, if one were to assume tenofovir tissue variability and compare MTN-024 (assuming N=11 due to 3:1 randomization) to MTN-013 (N=12 in each arm), then with 5% type I error and 80% power, we can exclude a difference as large as 1.23

SD units or a 275% difference. The sample size estimates are not different whether one assumes equal or unequal variance.

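### The PK comparison with MTN-013 is planned on raw means, and its detectable differences of 135% and 275% can describe only increases and rest on an implausible common SD; compare log concentrations and restate the figures as ratios

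*Protocol*

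**What the plan says.** Protocol 10.8.3 summarises end-of-period dapivirine concentrations by mean and SD and then states: "The population mean from this study will be compared to the population mean and standard deviation from similar end of period dapivirine results", for plasma, vaginal fluid and cervical tissue in MTN-013. It names no transformation and no test.

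Protocol 10.4.2 gives the planning figures.

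- **Vaginal fluid.** "The CV% ranges from 118% to 153% depending on time, location, and formulation". The calculation takes one value, "If one assumes a CV% of 130" percent, for a "comparison of MTN-013 (N=12) to MTN-024 (N=22"), and concludes: "then with 5% type I error and 80% power, we can exclude a difference as large as 1.04 SD units or a 135% difference".
- **Cervical tissue.** The section says published data are too few to estimate a CV and borrows one: "If this had the same variation as tenofovir in tissue, the CV% would be 210-240" percent. With group sizes given as "assuming N=11 due to 3:1 randomization) to MTN-013 (N=12 in each arm"), it concludes "then with 5% type I error and 80% power, we can exclude a difference as large as 1.23" SD units, or 275%.

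The section adds that assuming equal or unequal variance does not alter the sample size estimates. It states the intent as learning whether plasma and vaginal fluid concentrations differ between postmenopausal and premenopausal women, with no direction given.

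**The concern.** A concentration is positive. If its SD exceeds its mean, its distribution is strongly right-skewed: a normal model with CV 130% or 225% would put 22% or 33% of women below zero. Data of this kind usually have an SD that rises with the mean, which is also why variability is quoted as a CV. The planning figures assume instead that the SD stays fixed while the mean more than doubles (fluid) or nearly quadruples (tissue).

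Two further points need no model. No concentration can fall by 135% or 275%, so the quoted differences say nothing about lower exposure. And 80% power is the chance of detecting a difference of that size; what a study excludes is read from its confidence interval.

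The comparison of exposure between postmenopausal and premenopausal women is the stated intent behind the PK endpoint. If the planning figures are too optimistic, a null result could be over-read as evidence of similar exposure.

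**Working it through.** **Inputs (Protocol 10.4.2).** Fluid: 12 versus 22, CV 130% (range 118–153%). Tissue: 12 versus 11, CV 210–240%. Type I error 5%, power 80%. Sidedness is not stated; two-sided reproduces the figures.

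**Step 1: reproduce the plan.** For a two-sample t-test with a common SD, noncentrality is d × √(n₁n₂/(n₁+n₂)), where d is the difference in SD units. Solving for 80% power:

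- Fluid: d = 1.037; 1.037 × 130% = 134.8%. Power at 1.04 SD is 80.2%.
- Tissue: d = 1.226; 258% at CV 210%, 294% at CV 240%. Power at 1.23 SD is 80.2%. The stated 275% implies CV = 275/1.23 ≈ 224%.

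Both stated figures reproduce.

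**Step 2: what a common SD implies.** If the SD stays fixed while the MTN-024 mean rises by the stated amount, the MTN-024 CV becomes 130/2.35 ≈ 55% (fluid) and 224/3.75 ≈ 60% (tissue). Both lie far below every CV the section quotes.

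**Step 3: power with the same CV in both studies.** Assumption: lognormal data, SD(log) = √(ln(1+CV²)), giving 0.995 at CV 130% and 1.342 at CV 225%. Simulated power, two-sided 5%, at the stated increases:

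| Case | Pooled t, raw | Welch t, raw | t on logs |
|---|---|---|---|
| Fluid, 22 vs 12, ratio 2.35, CV 130% | 34% | 56% | 64% |
| Fluid, same, CV 118% to 153% | 42% to 25% | 63% to 47% | 70% to 56% |
| Tissue, 11 vs 12, ratio 3.75, CV about 225% | 33–34% | 25% | 61–62% |
| Tissue, same, CV 210% to 240% | 37% to 31% | 28% to 22% | 64% to 59% |

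For the inverse decreases, raw-mean power is 55% (pooled) or 31% (Welch) for fluid at ratio 0.43 and CV 130%, and 26–32% for tissue at ratio 0.27. The log test has the same power in both directions. Pooled and Welch results diverge clearly for fluid, so under this model the equal-or-unequal-variance sentence does not hold.

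**Step 4: sensitivity to the assumption.** With the same skewed shape but a common SD (a pure shift), the pooled raw t-test has 85% power for fluid at CV 130% and 88–90% for tissue. The shortfall therefore comes from the SD scaling with the mean, not from skewness alone.

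**Step 5: ratios detectable with 80% power on the log scale**, exp(±d × SD(log)):

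- Fluid, N=22: exp(1.037 × 0.995) ≈ 2.8, or 0.36.
- Fluid, N=34: d = 0.962; exp(0.962 × 0.995) ≈ 2.6, or 0.38. Protocol 7.7 and 10.4.2 give about 45 women providing fluid, and 45 × 3/4 = 33.75, so about 34 on dapivirine. The stated 22 is close to 30 × 3/4 = 22.5, the non-biopsy PK subset alone.
- Tissue, N=11, CV 210% to 240%: d = 1.226; 4.9 to 5.4, or 0.20 to 0.18.

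**The case against.** The planning figures are not miscalculated: they are exact for the common-SD t-test, and skewed data with a common SD keep about 80% power or more. A reader might infer that the plan simply fails to deliver its stated 80%. The documents do not support that unconditionally, because the shortfall rests on a constant-CV model that the protocol does not state. This stands, and the power loss is conditional. But the alternative requires MTN-024 CVs of about 55–60%, which nothing in 10.4.2 suggests.

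A reader might also infer that a raw-mean test cannot find a decrease. It can, as the powers above show; only the quoted percentages cannot describe one. Nor does moving to logs recover 80% at 135% or 275%. For fluid increases, the gain over Welch on raw means is modest (64% against 56%).

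The CV evidence is thin: the tissue range is borrowed from tenofovir and no plasma CV is given, so no power figure for plasma follows.

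Finally, 10.8.3 names no test, and an SAP that is not shown could set the log scale. That is fair for the choice of test, but it would not correct the claims printed in 10.4.2. The allowance for nonparametric methods in 10.8.2 is written for dapivirine versus placebo ring users, not for the MTN-013 comparison.

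**Conclusion.** The point holds in a conditional form. Without any model, the stated 135% and 275% describe increases only, although the aim has no direction, and the wording treats power to detect as ability to exclude. Given lognormal data with equal CV in both studies, raw-mean power at those differences is about 34% (pooled) or 56% (Welch) for fluid at 22 versus 12, and about 25–34% for tissue at 11 versus 12, instead of 80%. The protocol's own CVs make that assumption more plausible than a common SD, but they do not prove it. The log scale is the better basis, at about 64% and 62% for the same differences, so the detectable differences must be restated as well. This concerns a secondary, cross-study comparison and does not touch the primary safety analysis.

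**What to change.** - **10.8.3:** compare log-transformed concentrations and report the geometric mean ratio (MTN-024/MTN-013) with its 95% CI for each matrix.
- **10.4.2, detectable differences:** replace the percentages with ratios in both directions. Fluid: about 2.8-fold or 0.36 at the stated N=22, or about 2.6-fold or 0.38 if N=34 is intended; say which N applies. Tissue: about 4.9- to 5.4-fold, or 0.20 to 0.18, for CV 210–240%. State the lognormal, equal-CV assumption.
- **10.4.2, wording:** say *detect* instead of *exclude*, and judge what is excluded from the interval. Delete or qualify the sentence on equal and unequal variance.

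**Cost.** No extra participants or samples. The analysis needs individual or log-scale MTN-013 data; 10.8.3 mentions only that study's mean and SD, and the protocol does not say whether more is available. It also needs a rule for values below the assay limit, and results will be on the geometric-mean scale. The restated ratios are wide, especially for tissue, and show more openly how little this comparison can resolve.

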10.8.4 Missing Data

In any situation with missing data, an appropriate secondary analyses will be performed to adjust for variables that may be related to the missingness mechanism. If missing data rates are higher than 10%, covariates that are related to missingness in likelihood-based regression models will be included. A sensitivity analyses to assess the potential impact of the missing data will also be performed. These analyses will include imputing the data under the most extreme scenarios of information missingness, such as assuming everyone missing has an extreme value of the missing variable, and less informative imputation approaches.

11 DATA HANDLING AND RECORDKEEPING

11.1 Data Management Responsibilities

CRFs will be developed by the MTN SDMC in conjunction with the protocol team. Quality control reports and queries routinely will be generated and distributed by the SDMC to the study sites for verification and resolution. As part of the study activation process, each study site must identify all CRFs to be used as source documents. Data are transferred to the MTN SDMC, entered, and cleaned using the DataFax data management system.

11.2 Source Documents and Access to Source Data/Documents

All study sites will maintain source data/documents in accordance with current DAIDS policies.

(<http://www.niaid.nih.gov/labsandresources/resources/daidsclinrsrch/Pages/Default.aspx>)

Each IoR/designee will maintain, and store securely, complete, accurate and current study records throughout the study. In accordance with U.S. regulations regarding testing investigational products, the IoR/designee will maintain all study documentation for at least two years following the date of marketing approval for the study product being tested for the indication in which they were studied. If no marketing application is

filed, or if the application is not approved, the records will be retained for two years after the investigation is discontinued and the US FDA is notified.

Study records must be maintained on site for the entire period of study implementation. Thereafter, instructions for record storage will be provided by DAIDS. No study records may be moved to an off-site location or destroyed prior to receiving approval from DAIDS.

11.3 Quality Control and Quality Assurance

All study sites will conduct quality control and quality assurance procedures in accordance with current DAIDS policies.

(<http://www.niaid.nih.gov/labsandresources/resources/daidsclinrsrch/documents/qmppoicy.pdf>)

12 CLINICAL SITE MONITORING

Study monitoring will be carried out by Pharmaceutical Product Development, Inc. (PPD) (Wilmington, NC) in accordance with current DAIDS policies. On-site study monitoring will be performed in accordance with current DAIDS policies. Study monitors will visit the site to do the following:

- Review informed consent forms, procedures, and documentation
- Assess compliance with the study protocol, Good Clinical Practices (GCP) guidelines, and applicable regulatory requirements (US and non-US), including US CFR Title 45 Part 46 and Title 21 Parts 50, 56, and 312
- Perform source document verification to ensure the accuracy and completeness of study data
- Verify proper collection and storage of biological specimens
- Verify proper storage, dispensing, and accountability of investigational study products
- Assess implementation and documentation of internal site quality management procedures

The IoR/designee will allow study monitors to inspect study facilities and documentation (e.g., informed consent forms, clinic and laboratory records, other source documents, CRFs), as well as observe the performance of study procedures. The IoR/designee also will allow inspection of all study-related documentation by authorized representatives of the MTN Coordinating and Operations Center (CORE), SDMC, NL, IPM, NIAID, FDA, OHRP, IRBs and local and US regulatory authorities. A site visit log will be maintained at the study site to document all visits.

13 HUMAN SUBJECTS PROTECTIONS

Site investigators will make efforts to minimize risks to participants. Participants and study staff members will take part in a thorough informed consent process. Before beginning the study, the IoR/designee will have obtained IRB approval and the protocol will have been submitted to the FDA. The IoR/designee will permit audits by the NIH, IPM, the FDA, OHRP, MTN CORE, IRBs, SDMC, and other local and US regulatory authorities or any of their appointed agents.

13.1 Institutional Review Boards/Ethics Committees

Each participating institution is responsible for assuring that this protocol, the associated site-specific informed consent forms, and study-related documents (such as participant education and recruitment materials) are reviewed by an IRB responsible for oversight of research conducted at the study sites. Any amendments to the protocol must be approved by the responsible IRBs prior to implementation.

Subsequent to the initial review and approval, the responsible IRBs must review the study at least annually. Each IoR/designee will make safety and progress reports to the IRBs at least annually and within three months after study termination or completion. These reports will include the total number of participants enrolled in the study, the number of participants who completed the study, all changes in the research activity, and all unanticipated problems involving risks to human subjects or others. In addition, the results of all SMC reviews of the study will be provided to the IRBs. Study sites will submit documentation of continuing review to the DAIDS Protocol Registration Office in accordance with the DAIDS Protocol Registration Policy and Procedures Manual.

13.2 Protocol Registration

Prior to implementation of this protocol, and any subsequent full version amendments, each site must have the protocol and the protocol informed consent form(s) approved, as appropriate, by their local institutional review board (IRB)/ethics committee (EC) and any other applicable regulatory entity (RE). Upon receiving final approval, sites will submit all required protocol registration documents to the DAIDS Protocol Registration Office (DAIDS PRO) at the Regulatory Support Center (RSC). The DAIDS PRO will review the submitted protocol registration packet to ensure that all of the required documents have been received.

Site-specific informed consent forms (ICFs) *WILL* be reviewed and approved by the DAIDS PRO and sites will receive an Initial Registration Notification from the DAIDS PRO that indicates successful completion of the protocol registration process. A copy of the Initial Registration Notification should be retained in the site's regulatory files.

Upon receiving final IRB/EC and any other applicable RE approval(s) for an amendment, sites should implement the amendment immediately. Sites are required to submit an amendment registration packet to the DAIDS PRO at the RSC. The DAIDS

PRO will review the submitted protocol registration packet to ensure that all the required documents have been received. Site-specific ICF(s) *WILL NOT* be reviewed and approved by the DAIDS PRO and sites will receive an Amendment Registration Notification when the DAIDS PRO receives a complete registration packet. A copy of the Amendment Registration Notification should be retained in the site's regulatory files.

For additional information on the protocol registration process and specific documents required for initial and amendment registrations, refer to the current version of the DAIDS Protocol Registration Manual.

13.3 Study Coordination

IPM holds the Investigational New Drug (IND) application for this study. Copies of all regulatory documents submitted to this IND by IPM are forwarded to DAIDS. Assignment of all sponsor responsibilities for this study will be specified in a Clinical Trial Agreement (CTA) executed by NIAID and IPM.

Study implementation will also be guided by a common study-specific procedures manual that provides further instructions and operational guidance on conducting study visits; data and forms processing; specimen collection, processing, and shipping; AE assessment, management and reporting; dispensing study products and documenting product accountability; and other study operations. Standardized study-specific training will be provided to all sites by the MTN CORE, SDMC, NL and other designated members of the Protocol Team.

Close coordination between protocol team members is necessary to track study progress, respond to queries about proper study implementation, and address other issues in a timely manner. The PSRT will address issues related to study eligibility and AE management and reporting as needed to assure consistent case management, documentation, and information-sharing across sites. Rates of accrual, adherence, follow-up, and AE incidence will be monitored closely by the team as well as the SMC.

13.4 Risk Benefit Statement

13.4.1 Risks

General

It is not expected that this trial will expose human subjects to unreasonable risk.

Pelvic examination and procedures may cause mild discomfort, pressure and/or vaginal bleeding or spotting. Phlebotomy may lead to discomfort, feelings of dizziness or faintness, and/or bruising, swelling and/or infection. Disclosure of HIV and STI status may cause worry, sadness or depression. Disclosure of HIV-positive status has been associated with depression, suicidal ideation, and denial as well as social isolation. Trained counselors will be available to help participants deal with these feelings.

Participation in clinical research includes the risks of loss of confidentiality and discomfort with the personal nature of questions when discussing sexual behaviors.

Participants at sites where local regulatory authorities require partner notification in response to diagnosed STI or HIV infection could have problems in their relationships with their sexual partners. Participants also could have problems in their partner relationships associated with use of study product.

Use of the study VR may lead to vaginal symptoms, including irritation, increased discharge, and discomfort (including with vaginal intercourse). It is possible that a participant may have an allergic reaction to the study product. Symptoms of an allergic reaction include rash or other skin irritation, itching, joint pain, or difficulty in breathing.

Based on AEs reported among female participants in previous studies, dapivirine VRs may be associated with:

- Vaginal candidiasis
- Vaginal bleeding
- Headache
- Fatigue
- Vulvovaginal or genital itching
- Abdominal discomfort
- Abdominal pain
- Urinary incontinence
- Nausea
- Vaginal or genital discharge

As with any vaginally retained product, the possibility of toxic shock syndrome, although rare, exists.

Cervical Biopsy Collection

For a subset of participants, cervical biopsies carry the risk of discomfort or pain during the procedure and for a few hours afterwards. Participants may have spotting (bleeding) for one or two days. Participants may also be at increased risk for STIs and HIV acquisition, if exposed. Participants will be instructed to refrain from sexual intercourse for 3 days before and after the collection of the biopsy. If participants engage in sexual intercourse before the biopsy has healed they may experience some temporary discomfort. There is a small risk of infection and heavier bleeding. Participants will be encouraged to call the clinic to report any AE after the collection, especially if heavy bleeding is noted (soaking through a pad or tampon in an hour or less) or if the participant develops any abnormal odor or discharge from the vagina.

Although study sites make every effort to protect participant privacy and confidentiality, it is possible that participants' involvement in the study could become known to others, and that social harms may result (i.e., because participants could become known as HIV-positive or at "high risk" for HIV infection). For example, participants could be

treated unfairly or discriminated against, or could have problems being accepted by their families and/or communities.

